6.12 Non Mayo Clinic sites

To register a patient, fax [REDACTED] a completed eligibility checklist to the Mayo Clinic Cancer Center (MCCC) Registration Office between 8 a.m. and 4:30 p.m. central time Monday through Friday.

6.13 (All Sites) Documentation of IRB approval must be on file in the Registration Office before an investigator may register any patients.

In addition to submitting initial IRB approval documents, ongoing IRB approval documentation must be on file (no less than annually) at the Registration Office (fax: [REDACTED]). If the necessary documentation is not submitted in advance of attempting patient registration, the registration will not be accepted and the patient may not be enrolled in the protocol until the situation is resolved.

When the study has been permanently closed to patient enrollment, submission of annual IRB approvals to the Registration Office is no longer necessary.

6.2 Verification

Prior to accepting the registration, registration/randomization application will verify the following:

- IRB approval at the registering institution
- Patient eligibility
- Existence of a signed consent form

- Existence of a signed authorization for use and disclosure of protected health information

6.3 Correlative Research

A mandatory correlative research component is part of this study, the patient will be automatically registered onto this component (see [Sections 3.19b](#) and [14.1](#)).

6.4 Documentation

Documentation of IRB approval must be on file in the Registration Office before an investigator may register any patients.

In addition to submitting initial IRB approval documents, ongoing IRB approval documentation must be on file (no less than annually) at the Registration Office ([contact]). If the necessary documentation is not submitted in advance of attempting patient registration, the registration will not be accepted and the patient may not be enrolled in the protocol until the situation is resolved.

When the study has been permanently closed to patient enrollment, submission of annual IRB approvals to the Registration Office is no longer necessary.

6.5 Treating institution

Treatment on this protocol must commence under the supervision of the hematologist from the enrolling institution.

6.6 Treatment start

Treatment cannot begin prior to registration and must begin ≤ 14 days after registration.

6.7 Pretreatment

Pretreatment tests/procedures (see Section 4.0) must be completed within the guidelines specified on the test schedule.

6.8 Baseline symptoms

All required baseline symptoms (see Section 10.62) must be documented and graded.

6.9 Study drug is available on site.

7.0 Protocol Treatment

7.1 Treatment Schedule

Table 7.1				
Agent	Dose Level	Route	Day	Retreatment
Ixazomib	4 mg	PO	1, 8, 15	Every 28 days
Pomalidomide	4 mg	PO	Days 1-21	Every 28 days
Dexamethasone	40 mg	PO	1, 8, 15, 22	Every 28 days

7.2 Dosing of ixazomib

The doses of ixazomib used in this study are based on data from Millennium's ongoing phase I and II trials, specifically the phase I/II trial of ixazomib (C16005) in combination with lenalidomide and dexamethasone, estimated 4 mg weekly of ixazomib as the RP2D in combination with weekly full dose of lenalidomide (25 mg) and dexamethasone (40 mg).

7.3 How to take ixazomib

The ixazomib should be taken on an empty stomach, at least 1 hour before or no sooner than 2 hours after a meal. Each capsule should be swallowed separately with a sip of water. A total of approximately 240 mL (about 1 cup/8 oz) of water should be taken with the capsules.

Missed doses can be taken as soon as the patient remembers as long as the next scheduled dose is 72 hours or more away. Patients who vomit a dose after ingestion will not receive an additional dose, but should resume dosing at the time of the next scheduled dose.

Drug will be administered only to eligible patients under the supervision of the investigator or identified sub-investigator(s). The drug will be prepared under the supervision of a pharmacist, or appropriately qualified and trained personnel.

7.4 Treatment at enrolling institution

As of Addendum 7, Mayo Rochester only

For this protocol, the patient must return to the consenting institution for evaluation at least every third cycle, provided the drug can be sent to the patient and necessary interval evaluations as required by the protocol can be completed remotely or through local healthcare facilities.

MMRC sites:

For this protocol, the patient must return to the consenting institution for evaluation at least every 28 days. Treatment by a local medical doctor (LMD) is not allowed.

7.5 Pomalidomide supply - POMALYST REMS™ program

All patients will be registered to the Celgene POMALYST REMS™ program to obtain pomalidomide, as required by the US Food and Drug Administration (FDA). Patients will receive pomalidomide every 28 days. All unused study drug must be returned to Mayo

Clinic to be recorded. Study drug is to be handed back to the patient to return per POMALYST REMS™ policy. **Only enough pomalidomide for one cycle of therapy will be supplied to the patient each cycle.** See [Appendix IV](#) for pomalidomide information.

8.0 Dosage Modification Based on Adverse Events

Strictly follow the modifications in this table for the first **two** cycles, until individual treatment tolerance can be ascertained. Individual drugs can be dose reduced as per the table below depending on the adverse event attribution. Thereafter, these modifications should be regarded as guidelines to produce mild-to-moderate, but not debilitating, side effects. If multiple adverse events are seen, administer dose based on greatest reduction required for any single adverse event observed. Reductions apply to treatment given in the preceding cycle and are based on adverse events observed since the prior dose.

NOTE: If either of pomalidomide or ixazomib is discontinued, the patient can continue on the other drugs, unless specified otherwise in the dose modification tables. If both are discontinued, the patient will go to event monitoring (Section 18.0).

ALERT: ADR reporting may be required for some adverse events (See Section 10)

8.1 Dose Levels for each drug in the combination (Based on Adverse Events in Tables 8.2-4)

NOTE: One drug can be reduced each time based on the drug most likely related to the toxicity observed.

Ixazomib (Days 1, 8, 15)		Pomalidomide (Day 1-21)		Dexamethasone (Days 1, 8, 15, 22)	
Starting dose	4 mg	Starting dose	4 mg	Starting dose	40 mg
-1	3 mg	-1	3 mg	-1	20 mg
-2	2.3 mg	-2	2 mg	-2	12 mg
-3	2.3 mg days 1, 15	-3	1 mg	-3	4 mg
-4	Discontinue	-4	Discontinue	-4	Discontinue

If patients cannot tolerate dose level – 3 of ixazomib AND pomalidomide they will go to event monitoring per Section 18.0. If dexamethasone is discontinued, the patient may continue treatment.

8.11 Instruction for initiation of a new cycle of therapy

A new cycle of treatment may begin on the scheduled Day 1 of a new cycle if:

- The ANC is $\geq 1000/\mu\text{L}$
- The platelet count is $\geq 50,000/\mu\text{L}$
- Any other non-hematologic treatment -related adverse event that may have occurred has resolved to \leq Grade 1 or baseline severity.

If these conditions are not met on Day 1 of a new cycle, the subject will be evaluated weekly and a new cycle of therapy will be held until the toxicity has resolved as described above.

If any drug dosing was halted during the previous cycle and was restarted with a one-level dose reduction without requiring an interruption for the remainder of the cycle, then that reduced dose level will be initiated on Day 1 of the new cycle.

If any drug dosing was omitted for the remainder of the previous cycle or if the new cycle is held due to known hematologic toxicity newly encountered on the scheduled Day 1, then the new cycle will be started with a one-level dose reduction. If a new cycle of therapy cannot be restarted within 4 weeks of the scheduled Day 1 due to non-resolution of drug related toxicities, the patient will be removed from protocol therapy and will go to event monitoring.

→ → Use the NCI Common Terminology Criteria for Adverse Events (CTCAE) version 4.0* unless otherwise specified ← ←

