8.2 Dose modifications for ixazomib based on adverse events during a cycle

CTCAE System/Organ/Class (SOC)	ADVERSE EVENT	AGENT[#]	ACTION**
Investigations	If platelet count $<30 \times 10^9/L$ or ANC $<1.0 \times 10^9/L$ or ANC $>1.0 \times 10^9/L$ (up to LLN) with fever (temperature $>38.5^\circ C$)	Ixazomib	Days 2-15: Ixazomib dose should be omitted. Complete blood count (CBC) with differential should be followed weekly. If ANC is $\geq 1.0 \times 10^9/L$ and/or platelet counts $\geq 30 \times 10^9/L$, ixazomib may be reinitiated with 1 dose level reduction (see Table 8.1). The subsequent cycle will use the reduced dose.
Skin and subcutaneous tissue disorders	Rash, maculopapular, \geq Grade 2	Ixazomib	Omit ixazomib till rash resolves to \leq Grade 1 (See Section 9.9a). Restart at same dose. If the rash recurs, reduce dose by one dose level.
	Any skin, Grade 4		Discontinue ixazomib
Nervous System Disorders	Newly developed Grade 1 peripheral neuropathy with pain, \geq Grade 2 peripheral neuropathy,	Ixazomib	Reduce dose of ixazomib to the next lower dose level
	Grade 2 neuropathy with pain or Grade 3 peripheral neuropathy	Ixazomib	Omit ixazomib until toxicity resolves or returns to baseline. When toxicity resolves, re-initiate ixazomib at the next lower dose level.

Table 8.2			
CTCAE System/Organ/Class (SOC)	ADVERSE EVENT	AGENT[#]	ACTION^{**}
	Grade 4 peripheral neuropathy	Ixazomib	Omit ixazomib. Peripheral neuropathy should be monitored until toxicity resolves or returns to baseline. Upon recovery, if the patient has received clinical benefit from therapy with ixazomib, the investigator may consider restarting ixazomib at the next lower dose level.
Other	Any other non-hematological Grade 3 attributable toxicity except: Grade 3 nausea and/or emesis in the absence of optimal anti-emetic prophylaxis Grade 3 diarrhea that occurs in the absence of optimal supportive therapy Grade 3 fatigue	Ixazomib Pomalidomide	Omit ixazomib or pomalidomide or both depending on the attribution to either or both drugs, until resolution to Grade ≤ 1 or baseline Restart at next lower dose - If a patient is already at the lowest drug level, go to event monitoring If the toxicity can be attributed to either of the drugs, pomalidomide should be discontinued at first instance followed by ixazomib for recurrence of the same toxicity necessitating dose modification

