	Grade 4 Nonhematologic Toxicities	Ixazomib Pomalidomide	Permanently discontinue pomalidomide. Consider permanently discontinuing ixazomib – Exception if the investigator determines the patient is obtaining a clinical benefit If both ixazomib and pomalidomide are discontinued, the patient will go to event monitoring

* Located [REDACTED]

** Use the following to describe actions in the Action column:

- Omit = The current dose(s) for the specified drug(s) during a cycle is skipped. The patient does not make up the omitted dose(s) at a later time
- Hold/Delay = The current dose(s) of all drugs during a cycle is delayed. The patient does make up the delayed dose(s) when the patient meets the protocol criteria to restart drugs.
- Discontinue = The specified drug(s) are totally stopped.

NOTE: For toxicities attributable to both ixazomib and pomalidomide, only one of the drugs should be reduced for each incidence of toxicity severe enough to necessitate dose reduction. The drug reduced should alternate starting with pomalidomide for the first dose reduction.

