8.4 Dose modifications for dexamethasone based on adverse events during a cycle

Table 8.4			
CTCAE System/Organ/Class (SOC)	ADVERSE EVENT	AGENT	ACTION**
BASED ON INTERVAL ADVERSE EVENT (Days 2-28 of each cycle)			
Gastrointestinal disorders	Dyspepsia, gastric or duodenal ulcer, gastritis Grade 1-2 (Symptomatic; altered GI function; medical intervention indicated; limiting instrumental ADL)	Dexamethasone	Treat with H2 blockers, sucralfate, or omeprazole If symptoms persist despite above measures, decrease dexamethasone dose by 1 dose level
	Dyspepsia, gastric or duodenal ulcer, gastritis ≥Grade 3 (Severely altered GI function; TPN indicated; elective operative or endoscopic intervention indicated; limiting self-care ADL; disabling)	Dexamethasone	Omit dexamethasone until symptoms adequately controlled Restart one dose level below along with concurrent therapy with H2 blockers, sucralfate, or omeprazole If symptoms persist despite above measures, discontinue dexamethasone and do not resume Ixazomib and pomalidomide should be continued
	Pancreatitis ≥Grade 3 (Severe pain; vomiting; medical intervention indicated (e.g., analgesia, nutritional support))	Dexamethasone	Discontinue dexamethasone and do not resume Ixazomib and pomalidomide should be continued
General disorders and administration site conditions	Edema ≥Grade 3 (limiting function and unresponsive to therapy or anasarca)	Dexamethasone	Diuretics as needed, and decrease dexamethasone dose by 1 dose level If edema persists despite above measures, decrease dose another dose level Discontinue dexamethasone and do not resume if symptoms persist despite second reduction Ixazomib and pomalidomide should be continued

CTCAE System/Organ/Class (SOC)	ADVERSE EVENT	AGENT	ACTION**
Psychiatric disorders	Confusion or Mood alteration ≥Grade 2 (Severe disorientation; limiting self-care ADL)	Dexamethasone	Omit dexamethasone until symptoms resolve Restart with one dose level reduction If symptoms persist despite above measures, discontinue dexamethasone and do not resume Ixazomib and pomalidomide should be continued
Musculoskeletal and connective tissue disorders	Muscle weakness ≥ Grade 2 Weakness limiting self-care ADL; disabling	Dexamethasone	Decrease dexamethasone dose by one dose level; if weakness persists despite above measures decrease dose by one additional dose level Discontinue dexamethasone and do not resume if symptoms continue to persist Ixazomib and pomalidomide should be continued

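### Section 8.11 and the dose modification tables give opposite outcomes for new treatment-related events that persist at Grade 2 or higher to the next Day 1

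*Combined protocol and SAP*

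**What the plan says.** Section 8.11 sets the conditions for Day 1 of a new cycle. Besides the blood-count limits it requires the following: "Any other non-hematologic treatment -related adverse event that may have occurred has resolved to" Grade 1 or lower, or baseline severity. If this fails, "the subject will be evaluated weekly and a new cycle of therapy will be held until the toxicity has resolved as described above". The footnotes to the tables define a hold as covering the whole regimen: "Hold/Delay = The current dose(s) of all drugs during a cycle is delayed". The limit then follows: "If a new cycle of therapy cannot be restarted within 4 weeks of the scheduled Day 1 due to non-resolution of drug related toxicities". In that case protocol therapy ends and event monitoring begins. No drug, event or attribution is exempted.

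The tables deal with some of the same events one drug at a time:

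- **Table 8.2, neuropathy of Grade 2 or higher.** The action is "Reduce dose of ixazomib to the next lower dose level". Grade 2 with pain and Grade 3 have their own row, which does omit ixazomib, as does the Grade 4 row. The reduction-only action is therefore what applies to painless Grade 2.
- **Table 8.4, muscle weakness of Grade 2 or higher.** The first steps are "Decrease dexamethasone dose by one dose level; if weakness persists despite above measures decrease dose by one additional dose level". If that fails: "Discontinue dexamethasone and do not resume if symptoms continue to persist Ixazomib and pomalidomide should be continued".
- **Table 8.4, confusion or mood alteration of Grade 2 or higher.** Dexamethasone is omitted, then restarted lower, then stopped for good if symptoms persist. The other two drugs go on.
- **Table 8.3, other non-hematologic events of Grade 3 or higher.** Pomalidomide is omitted, then restarted one level lower once the event is at Grade 2 or lower before Day 21.

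The NOTE in Section 8.0 adds: "If either of pomalidomide or ixazomib is discontinued, the patient can continue on the other drugs", unless the tables specify otherwise. Section 8.1 says that treatment may continue if dexamethasone is discontinued.

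**The concern.** A patient with one of these events can be kept on two or three drugs by the table and taken off all of them by Section 8.11. Two sites that both follow the protocol could treat the same patient in opposite ways.

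This bears on the primary endpoint. A success needs a response on two consecutive evaluations (Section 16.11), and EMD is imaged at the end of Cycle 1 and then every three cycles. A patient removed between two scans loses the scheduled confirming scan but remains evaluable. Which rule a site applies can therefore influence whether an EMD response is counted.

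**Working it through.** No figure in the plan needs reproducing. The check sets the texts side by side for an event that is new or worse than baseline, treatment-related, and still above Grade 1 on the next scheduled Day 1.

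| Event still present on Day 1 | Table action | Section 8.11 action |
|---|---|---|
| Painless Grade 2 neuropathy | Ixazomib one level lower; no omission, no wait for resolution | Hold all drugs; remove after 4 weeks |
| Muscle weakness, Grade 2 or higher | Reduce, then stop dexamethasone; other two drugs continue | Hold all drugs; remove after 4 weeks |
| Confusion or mood alteration, Grade 2 or higher | Omit, restart lower, then stop dexamethasone; other two drugs continue | Hold all drugs; remove after 4 weeks |
| Other non-hematologic event, Grade 3 reduced to Grade 2 | Pomalidomide already restarted one level lower | Hold all drugs; remove after 4 weeks |

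For the last row, Table 8.2 has its own entry for other Grade 3 non-hematologic events. It also names pomalidomide and waits for Grade 1 or baseline, so the two tables differ from each other there as well.

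**Timing, from 28-day cycles.** Suppose painless Grade 2 neuropathy appears in Cycle 1 and does not improve. Cycle 2 Day 1 falls on day 1 + 28 = 29. Section 8.11 holds the cycle, and the limit is reached on day 29 + 28 = 57. Under Table 8.2 alone, the same patient would be in or past Cycle 2 at the reduced ixazomib level.

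**Where the event is graded.** The test schedule places on-treatment adverse event monitoring and physical examination at the pre-treatment visit of each cycle. The Day 8, 15 and 22 column carries only a blood count. Neuropathy or weakness will therefore often be graded at the Day 1 visit, where the two rules meet.

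**Consequence for response confirmation.** The first EMD scan is at the end of Cycle 1 and the next at the end of Cycle 1 + 3 = 4. Three Day 1 checks (Cycles 2, 3 and 4) lie around or between them, and removal at any of these means that the second scheduled scan is not reached. The End of Treatment column has no EMD imaging, and the event-monitoring schedule in Section 4.2 lists no disease tests. The patient stays in the denominator under Section 16.11.

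In the full set of 27, each unconfirmed response lowers the estimate by 1/27 = 3.7 percentage points. The final rule turns on 10 against 9 successes of 27 (37.0% against 33.3%), and the interim rule on 3 against 2 of 10. One patient matters only if the count lies at the boundary.

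**The case against.** The best defence is that the rules apply at different times. Tables 8.2 to 8.4 are each headed as covering events during a cycle, Table 8.4 is limited to Days 2-28, and Section 8.11 governs Day 1. The endocrine row of Table 8.3 even sends the reader to the new-cycle instructions, which suggests that the two were meant to run in sequence. After two cycles the modifications become guidance rather than strict rules.

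This narrows the point but does not remove it. Stopping dexamethasone for good while the other drugs continue is an instruction that runs past the end of the cycle. So is a lower ixazomib level with no wait for resolution. The cross-reference in the endocrine row concerns that row only. The softer status begins after the first two cycles, so the conflict at Cycle 2 Day 1 is within the strict period, and it is unclear whether the softening reaches Section 8.11 at all.

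Several stronger readings are tempting, and the documents do not support them:

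- **That all Grade 2 events are affected.** Table 8.2 omits ixazomib for Grade 2 maculopapular rash until Grade 1 or lower, and for painful Grade 2 neuropathy until resolution or baseline. Events at baseline severity satisfy Section 8.11, and the exclusion criteria allow painless Grade 2 neuropathy at entry.
- **That the NOTE in Section 8.0 contradicts Section 8.11.** It is a permission, which can coexist with a Day 1 check. What is missing is a clarification.
- **That removal rules out confirmation or loses progression.** Table 11.5, footnote a, allows confirmation at any time before new therapy. End of Treatment includes serum electrophoresis, event monitoring runs every 3 months until progression, and Section 18.5 covers documentation of progression. Only the scheduled EMD confirmation is lost.
- **That the events are minor.** Table 8.4 describes its weakness row as disabling and as limiting self-care.

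**Conclusion.** The conflict is real for new or worsened treatment-related events that persist at Grade 2 or higher to Day 1. It covers painless Grade 2 neuropathy (Table 8.2), muscle weakness and confusion or mood alteration (Table 8.4), and the differing Grade 2 threshold for other non-hematologic events (Table 8.3). No text gives precedence or exempts an event already acted on under a table.

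Its frequency cannot be stated. A reader might start from the 26% peripheral neuropathy in Table 1-3. That figure is all-grade, pools other regimens (some with twice-weekly ixazomib), and is reported irrespective of causality. It says nothing about pain or persistence. The 44% for fatigue does not help either, because neither Table 8.2 nor Table 8.4 has a Grade 2 fatigue row.

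The effect on the endpoint rests on two assumptions: the patient's response depends on EMD imaging, and no unscheduled scan is done before new therapy.

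**What to change.** Reconcile Section 8.11 with Tables 8.2, 8.3 and 8.4 and the notes in Sections 8.0 and 8.1, so that the text gives one outcome per patient. It should state:

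1. which text governs on Day 1 when an event has already been acted on under a table and persists;
2. whether the Day 1 criterion and the 4-week limit apply to the whole regimen or only to the drug to which the event is attributed;
3. as a clarification, whether an event due to a drug already stopped still counts;
4. whether the guidance status after two cycles extends to Section 8.11.

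Which rule to adopt is a clinical decision for the study team, and this review takes no position on it. The cost is revised wording in Section 8.11 and cross-references in the tables. It needs no extra patients, visits or tests.

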8.2 Dose modifications for ixazomib based on adverse events during a cycle

CTCAE System/Organ/Class (SOC)	ADVERSE EVENT	AGENT[#]	ACTION**
Investigations	If platelet count $<30 \times 10^9/L$ or ANC $<1.0 \times 10^9/L$ or ANC $>1.0 \times 10^9/L$ (up to LLN) with fever (temperature $>38.5^\circ C$)	Ixazomib	Days 2-15: Ixazomib dose should be omitted. Complete blood count (CBC) with differential should be followed weekly. If ANC is $\geq 1.0 \times 10^9/L$ and/or platelet counts $\geq 30 \times 10^9/L$, ixazomib may be reinitiated with 1 dose level reduction (see Table 8.1). The subsequent cycle will use the reduced dose.
Skin and subcutaneous tissue disorders	Rash, maculopapular, \geq Grade 2	Ixazomib	Omit ixazomib till rash resolves to \leq Grade 1 (See Section 9.9a). Restart at same dose. If the rash recurs, reduce dose by one dose level.
	Any skin, Grade 4		Discontinue ixazomib
Nervous System Disorders	Newly developed Grade 1 peripheral neuropathy with pain, \geq Grade 2 peripheral neuropathy,	Ixazomib	Reduce dose of ixazomib to the next lower dose level
	Grade 2 neuropathy with pain or Grade 3 peripheral neuropathy	Ixazomib	Omit ixazomib until toxicity resolves or returns to baseline. When toxicity resolves, re-initiate ixazomib at the next lower dose level.

Table 8.2			
CTCAE System/Organ/Class (SOC)	ADVERSE EVENT	AGENT[#]	ACTION^{**}
	Grade 4 peripheral neuropathy	Ixazomib	Omit ixazomib. Peripheral neuropathy should be monitored until toxicity resolves or returns to baseline. Upon recovery, if the patient has received clinical benefit from therapy with ixazomib, the investigator may consider restarting ixazomib at the next lower dose level.
Other	Any other non-hematological Grade 3 attributable toxicity except: Grade 3 nausea and/or emesis in the absence of optimal anti-emetic prophylaxis Grade 3 diarrhea that occurs in the absence of optimal supportive therapy Grade 3 fatigue	Ixazomib Pomalidomide	Omit ixazomib or pomalidomide or both depending on the attribution to either or both drugs, until resolution to Grade ≤ 1 or baseline Restart at next lower dose - If a patient is already at the lowest drug level, go to event monitoring If the toxicity can be attributed to either of the drugs, pomalidomide should be discontinued at first instance followed by ixazomib for recurrence of the same toxicity necessitating dose modification
	Grade 4 Nonhematologic Toxicities	Ixazomib Pomalidomide	Permanently discontinue pomalidomide. Consider permanently discontinuing ixazomib – Exception if the investigator determines the patient is obtaining a clinical benefit If both ixazomib and pomalidomide are discontinued, the patient will go to event monitoring

* Located [REDACTED]

** Use the following to describe actions in the Action column:

- Omit = The current dose(s) for the specified drug(s) during a cycle is skipped. The patient does not make up the omitted dose(s) at a later time
- Hold/Delay = The current dose(s) of all drugs during a cycle is delayed. The patient does make up the delayed dose(s) when the patient meets the protocol criteria to restart drugs.
- Discontinue = The specified drug(s) are totally stopped.

NOTE: For toxicities attributable to both ixazomib and pomalidomide, only one of the drugs should be reduced for each incidence of toxicity severe enough to necessitate dose reduction. The drug reduced should alternate starting with pomalidomide for the first dose reduction.

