In line with clinical practice, dermatology consult and biopsy of Grade 3 or higher rash or any SAE involving rash is recommended. Prophylactic measures should also be considered if a patient has previously developed a rash (e.g., using a thick, alcohol-free emollient cream on dry areas of the body or oral or topical antihistamines). A rare risk is Stevens-Johnson Syndrome, a severe and potentially life-threatening rash with skin peeling and mouth sores, which should be managed symptomatically according to standard medical practice. Punch biopsies for histopathological analysis are encouraged at the discretion of the investigator.

9.9b Thrombocytopenia

Blood counts should be monitored regularly as outlined in the protocol with additional testing obtained according to standard clinical practice. Thrombocytopenia may be severe but has been manageable with platelet transfusions according to standard clinical practice. Ixazomib administration should be modified as noted as per dose modification recommendations in the protocol when thrombocytopenia occurs (see [Table 8.2](#)). Therapy can be reinitiated at a reduced level upon recovery of platelet counts. A rare risk is thrombotic thrombocytopenic purpura (TTP), a rare blood disorder where blood clots form in small blood vessels throughout the body characterized by thrombocytopenia, petechiae, fever, or possibly more serious signs and symptoms. TTP should be managed symptomatically according to standard medical practice.

9.9c Neutropenia

Blood counts should be monitored regularly as outlined in the protocol with additional testing obtained according to standard clinical practice. Neutropenia may be severe but has been manageable. Growth factor support is not required but may be considered according to standard clinical practice. Ixazomib administration should be modified as noted as per dose modification recommendations in the protocol when neutropenia occurs (see [Table 8.2](#)). Therapy can be reinitiated at a reduced level upon recovery of ANC's.

9.9d Fluid Deficit

Dehydration should be avoided since ixazomib may cause vomiting, diarrhea, and dehydration. Acute renal failure has been reported in patients treated with ixazomib, commonly in the setting of the previously noted gastrointestinal toxicities and dehydration. Fluid deficit should be corrected before initiation of study drug and as needed during treatment to avoid dehydration.

9.9e Hypotension

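### Table 8.2, blood-count row: the ixazomib restart condition can be met while the reason for omission still holds, and the row does not say which instruction prevails (minor)

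*Combined protocol and SAP*

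**What the plan says.** Table 8.2 (Section 8.2), Investigations row, has a trigger and two actions.

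- **Trigger.** Any one of: platelets <30; ANC <1.0; or ANC >1.0 up to LLN with fever >38.5 °C (counts × 10⁹/L).
- **Omission.** "Days 2-15: Ixazomib dose should be omitted", with a weekly CBC afterwards.
- **Restart.** "If ANC is $\geq 1.0 \times 10^9/L$ and/or platelet counts $\geq 30 \times 10^9/L$, ixazomib may be reinitiated with 1 dose level reduction". Then: "The subsequent cycle will use the reduced dose".

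Other text bears on the row:

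- Section 8.0 makes the dose modifications strict for the first two cycles and a guideline after that.
- The definition under Table 8.2 says that an omitted dose is skipped and not made up.
- Section 8.11 starts with "A new cycle of treatment may begin on the scheduled Day 1 of a new cycle if" and lists ANC ≥1000/µL and platelets ≥50,000/µL together. If dosing was omitted for the rest of the previous cycle, "then the new cycle will be started with a one-level dose reduction".
- Section 9.9b on thrombocytopenia says: "Ixazomib administration should be modified as noted as per dose modification recommendations in the protocol when thrombocytopenia occurs". It points to Table 8.2 and adds: "Therapy can be reinitiated at a reduced level upon recovery of platelet counts". Section 9.9c says the same for ANC.
- The NOTE under Table 8.2 says that for toxicity attributable to both ixazomib and pomalidomide, only one drug is reduced per incidence, alternating and starting with pomalidomide.

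**The concern.** A restart rule should be the reverse of the rule that stopped the drug. Here three criteria joined by *or* stop ixazomib, but either of two count thresholds is enough to restart it, and fever has dropped out. A patient can meet the stopping rule and the restart rule on the same blood count.

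What is at stake is a dosing-safety instruction in the two cycles where it must be followed strictly. Two sites with identical Day 15 counts could act differently and both point to the same table cell. The platelet arm deserves a clear rule because Section 9.9h gives every patient daily aspirin, or anticoagulation if the thrombotic risk is high.

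**Working it through.** This is a question of rule logic, and the plan gives no figure to reproduce. The check sets the two conditions side by side and then traces which doses are exposed.

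**1. Trigger against restart.** All thresholds come from the row itself.

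| Counts (× 10⁹/L) | Trigger holds? | Restart, as written | Restart if and/or is read as *and* | Restart, proposed wording |
|---|---|---|---|---|
| Platelets 20, ANC 2.0 | Yes | Met, on ANC alone | Not met | Not met |
| Platelets ≥30, ANC <1.0 | Yes | Met, on platelets alone | Not met | Not met |
| Platelets ≥30, ANC >1.0 to LLN, fever | Yes | Met | Met | Not met |
| Platelets <30, ANC <1.0 | Yes | Not met | Not met | Not met |
| Platelets ≥30, ANC ≥1.0, no fever | No | Met | Met | Met |
| Platelets ≥30, ANC >LLN, fever | No | Met | Met | Met |

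The first three lines are the conflict. Changing and/or to *and* removes the first two but not the febrile one. The last two lines show that the proposed wording does not hold back a patient who is free of the triggers.

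**2. Comparison with neighbouring rules.** The other four omit-then-restart rows of Table 8.2 (rash, two neuropathy rows, other Grade 3 toxicity) make restart depend on the event that caused the omission; one neuropathy row reads "When toxicity resolves, re-initiate ixazomib at the next lower dose level". In Table 8.3, pomalidomide restarts when the platelet count or the neutropenia has resolved, which a count that never fell cannot do. Its febrile neutropenia row also requires the fever to have gone. The Table 8.2 blood-count row uses bare thresholds instead.

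The sentence in Section 8.0 about taking the greatest reduction when several events occur does not help. It sets the size of a reduction, not whether dosing resumes.

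**3. Doses exposed.**

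- Ixazomib is given on Days 1, 8 and 15 (Table 7.1), so only Days 8 and 15 fall in the Days 2-15 window.
- After a Day 8 omission, Day 15 is the only ixazomib dose left in that cycle.
- After a Day 15 omission, the next dose is Day 1 of a new cycle, where Section 8.11 requires both counts.
- At ixazomib level −3 (Days 1 and 15 only, Section 8.1) there is no Day 8 dose to omit.
- CBCs are scheduled on Days 8, 15 and 22 in Cycles 1-3 but only on Day 15 from Cycle 4 (Section 4.0). The exposure therefore lies mostly in the early cycles, which include the two strict ones.

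**4. Milligrams at stake.** These cannot be fixed. The row reduces ixazomib one level, from 4 mg to 3 mg at first occurrence (Section 8.1). If the toxicity is attributed to both drugs, the NOTE may direct the first reduction to pomalidomide, which would leave ixazomib at 4 mg. The documents do not say which instruction governs in this row.

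**5. Patients affected.** These cannot be estimated. Table 1-3 gives thrombocytopenia in 28% and neutropenia in 25% of 173 patients in oral combination studies, but for all grades. No rate is given below 30 or 1.0 × 10⁹/L.

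**The case against.** The strongest reply is that the row already blocks the feared dose. The trigger is not a one-time event. If platelets are still below 30 on Day 15, a day inside the window, the omission instruction applies again, while restart is only permitted, not required. The literal reading also proves too much: with platelets at 20 and ANC at 2.0, restart would be met on the very count that caused the omission, which would empty the first instruction of meaning. Sections 9.9b and 9.9c state the recovery condition in their own words.

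Much of this stands. The intent is evident, and most investigators would probably act on it. A reader might infer that the protocol plainly authorises ixazomib during persistent severe thrombocytopenia or neutropenia. The documents do not support that: the text is contradictory, not a clear permission.

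The reply does not remove the contradiction. Nothing in the cell says that the omission instruction outranks the restart sentence or that the trigger must be checked again. Sections 9.9b and 9.9c send the reader back to this table for the operative rule, and neither mentions restart after fever. Recovery of the affected count also leaves a gap when the other count has fallen by Day 15.

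**Conclusion.** Wrong as written, and minor: a defect in the wording of a dosing-safety rule. The restart sentence is not the complement of the trigger, and the row gives no precedence between its two instructions. The logic follows from the row's own thresholds and needs no outside assumption.

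The size is limited to mainly the Day 15 dose after a Day 8 omission, chiefly in the early cycles.

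Two stronger inferences should be resisted:

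- **A maximum excess dose or a fixed Cycle 2 starting dose.** Neither follows, because the drug to be reduced depends on attribution under the NOTE.
- **Damage to the early safety analysis or the efficacy decision.** Section 16.4 defines a DLT by the grade, duration and attribution of adverse events, and Section 16.2 decides on confirmed responses. Neither refers to this row, and the documents give no basis for an effect on DLT counts, alpha, power or the primary endpoint.

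**What to change.** Replace the restart sentence with:

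*Ixazomib may be restarted, with the one-level reduction, on a scheduled dosing day only when none of the omission criteria in this row is present, i.e. platelets ≥30 × 10⁹/L and ANC ≥1.0 × 10⁹/L and no fever >38.5 °C while ANC is at or below LLN.*

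This keeps the row's thresholds, covers a fever that first appears on Day 15, and does not bar a febrile patient whose ANC is above LLN. It also closes a small gap: the trigger speaks of ANC below 1.0 and above 1.0, so exactly 1.0 with fever is not addressed, and the new wording places it in the febrile band.

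The change is one sentence in one table cell and can wait for the next amendment. It needs no extra tests, since the row already calls for weekly CBCs after an omission. The downside is that an occasional Day 15 dose is skipped that a literal reading would have allowed.
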